7.3.5. Safety Events of Interest

The identification of safety events of interest should be identified by the study site and communicated to Pfizer or designee. These safety events may also be identified by the Pfizer Study Team or designee during the review of subject data listings or by site monitors during routine monitoring of subject study records.

The Pfizer Study Team or designee will provide a listing of specific documents needed to support event adjudication by the Adjudication Committees (see [Section 9.7](#) Safety Event Adjudication Committees). Obtaining and submitting the documentation will be the responsibility of the study site. Event documentation will vary with the event requiring adjudication and may include (but not be limited to): hospital discharge summaries, operative reports, clinic notes, electrocardiograms (ECGs), diagnostic tests, pathology reports, autopsy reports and death certificate information, as applicable.

When there is a decision to biopsy a potentially malignant tumour, lymph node, or other tissue, the investigator and/or consultant(s) should contact Pfizer or designee to discuss the issue and any decisions as soon as possible. For all biopsies of potentially malignant tumours, suspicious lymphadenopathy, or possible extranodal lymphoproliferative disorder (LPD), the study site will request the pathologist to send the original slides used to make the definitive diagnosis, ancillary study reports, and the pathologist's report to the central laboratory for a blinded review by a central pathologist. See [Appendix 5](#) for the steps to take in the event of potentially malignant tumours, lymphadenopathy or possible extra-nodal LPD which might arise in the course of this study. See [Appendix 6](#) for the steps to take when gastrointestinal tract biopsies are obtained.

7.3.6. Risk Factor Check for Venous Thromboembolism

All subjects will undergo a risk factor check at each study visit to check for newly-developed risk factors for venous thromboembolism. This information is to be captured in the subject's source file and on the relevant case report form.

A subject may be at high risk for venous thromboembolism if he/she:

- has heart failure or prior myocardial infarction within the past 3 months;
- has inherited coagulation disorders;
- has had venous thromboembolism, either deep venous thrombosis or pulmonary embolism;
- is taking combined hormonal contraceptives or hormone replacement therapy;

- has malignancy (association is strongest with cancers other than non-melanoma skin cancers);
- is undergoing major surgery or is immobilized.

If a subject is receiving blinded tofacitinib or open-label 10 mg BID and has one or more of the risk factors for venous thromboembolism listed above, the subject's tofacitinib dose should be adjusted to open-label 5 mg BID. If a subject has any newly-developed risk factors for venous thromboembolism identified during the study, they will not be permitted to receive tofacitinib 10 mg BID.

If a subject is receiving tofacitinib open-label 5 mg BID and has one or more of the risk factors for venous thromboembolism listed above, they may remain on tofacitinib open-label 5 mg BID after careful investigator assessment of benefit:risk. However, he/she will not be permitted to increase their dose of tofacitinib to 10 mg BID if he/she experiences a flare of their UC disease (see [Section 5.11](#)).

Lastly, if a subject has any of the risk factors listed above, the subject will not be eligible to enroll in Study A3921288, per Amendment 2.

Additional risk factors for venous thromboembolism, such as age, diabetes, obesity (BMI>30), smoking status, hypertension, and first degree family history of venous thromboembolism should also be taken into consideration by the investigator and the Sponsor medical monitor when evaluating the benefit:risk for each individual subject whether to modify their dose of tofacitinib.

8. ADVERSE EVENT REPORTING

8.1. Requirements

The table below summarizes the requirements for recording safety events on the CRF and for reporting safety events on the Clinical Trial (CT) Serious Adverse Event (SAE) Report Form to Pfizer Safety. These requirements are delineated for 3 types of events: (1) SAEs; (2) non-serious adverse events (AEs); and (3) exposure to the investigational product under study during pregnancy or breastfeeding, and occupational exposure.

Safety Event	Recorded on the CRF	Reported on the CT SAE Report Form to Pfizer Safety Within 24 Hours of Awareness
SAE	All	All
Non-serious AE	All	None
Exposure to the investigational product under study during pregnancy or breastfeeding, and occupational exposure	All (regardless of whether associated with an AE), except occupational exposure	Exposure during pregnancy, exposure via breastfeeding, occupational exposure (regardless of whether associated with an AE)

All observed or volunteered events regardless of treatment group or suspected causal relationship to the investigational product(s) will be reported as described in the following paragraphs.

Events listed in the table above that require reporting to Pfizer Safety on the CT SAE Report Form within 24 hours of awareness of the event by the investigator **are to be reported regardless of whether the event is determined by the investigator to be related to an investigational product under study**. In particular, if the SAE is fatal or life-threatening, notification to Pfizer Safety must be made immediately, irrespective of the extent of available event information. This time frame also applies to additional new (follow-up) information on previously forwarded reports. In the rare situation that the investigator does not become immediately aware of the occurrence of an event, the investigator must report the event within 24 hours after learning of it and document the time of his/her first awareness of the event.

For each event, the investigator must pursue and obtain adequate information both to determine the outcome and to assess whether it meets the criteria for classification as an SAE (see the [Serious Adverse Events](#) section below). In addition, the investigator may be requested by Pfizer Safety to obtain specific follow-up information in an expedited fashion. This information is more detailed than that recorded on the CRF. In general, this will include a description of the event in sufficient detail to allow for a complete medical assessment of the case and independent determination of possible causality. Any information relevant to the event, such as concomitant medications and illnesses, must be provided. In the case of a subject death, a summary of available autopsy findings must be submitted as soon as possible to Pfizer Safety. Any pertinent additional information must be reported on the CT SAE Report Form; additional source documents (eg, medical records, CRF, laboratory data) are to be sent to Pfizer Safety **ONLY** upon request.

As part of ongoing safety reviews conducted by the sponsor, any non-serious AE that is determined by the sponsor to be serious will be reported by the sponsor as an SAE. To assist in the determination of case seriousness, further information may be requested from the investigator to provide clarity and understanding of the event in the context of the clinical study.

8.1.1. Additional Details On Recording Adverse Events on the CRF

All events detailed in the table above will be recorded on the AE page(s) of the CRF. It should be noted that the CT SAE Report Form for reporting of SAE information is not the same as the AE page of the CRF. When the same data are collected, the forms must be completed in a consistent manner. AEs should be recorded using concise medical terminology and the same AE term should be used on both the CRF and the CT SAE Report Form for reporting of SAE information.

8.1.2. Eliciting Adverse Event Information

The investigator is to record on the CRF all directly observed AEs and all AEs spontaneously reported by the study subject. In addition, each study subject will be questioned about the occurrence of AEs in a non-leading manner.

8.1.3. Withdrawal From the Study Due to Adverse Events (see also the [Subject Withdrawal](#) section)

Withdrawal due to AEs should be distinguished from withdrawal due to other causes, according to the definition of AE noted below, and recorded on the CRF.

When a subject withdraws from the study because of an SAE, the SAE must be recorded on the CRF and reported, as appropriate, on the CT SAE Report Form, in accordance with the [Requirements](#) section above.

8.1.4. Time Period for Collecting AE/SAE Information

The time period for actively eliciting and collecting AEs and SAEs (“active collection period”) for each subject begins from the time the subject provides informed consent, which is obtained before the subject’s participation in the study (ie, before undergoing any study-related procedure and/or receiving investigational product), through and including a minimum of 28 calendar days; except as indicated below after the last administration of the investigational product.

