The investigator may schedule visits (unplanned visits) in addition to those listed on the schedule of activities table, in order to conduct evaluations or assessments required to protect the well-being of the subject.

All study visits after Baseline will have a visit window of ± 7 days.

Refer to [Appendix 9](#) for permitted alternative measures for certain study procedures in response to the ongoing global COVID-19 pandemic.

Study Procedure	Baseline	Treatment Period						
	Day 1 ¹	Month 1 (± 7 days)	Month 3 (± 7 days)	Month 6 (± 7 days)	Month 9 (± 7 days)	Month 12 (± 7 days)	Month 15 (± 7 days)	Month 18 (± 7 days)
Visit Number	1	2	3	4	5	6	7	8
Informed Consent	X							
Medical History ²	X							
Demography ¹⁰	X							
Targeted Physical Examination ³	OLE	X	X	X	X	X	X	X
Vital Signs, Including Temperature	OLE	X	X	X	X	X	X	X
Laboratory								
Hematology	OLE	X	X	X	X	X	X	X
Serum Chemistry	OLE	X	X	X	X	X	X	X
Lipid Profile, Fasting	OLE			X		X		X
Urine β -hCG ⁴	OLE	X	X	X	X	X	X	X
Dispense Stool Sample Collection Kit	X	X	X	X	X	X	X	X
Collect Stool Sample for Fecal Calprotectin ⁵	X	X	X	X	X	X	X	X
High-Sensitivity CRP	OLE	X	X	X	X	X	X	X
Tuberculosis Testing/Chest Radiograph, if necessary in Specific Countries ⁶						X		

Study Procedure	Baseline	Treatment Period						
	Day 1 ¹	Month 1 (±7 days)	Month 3 (±7 days)	Month 6 (±7 days)	Month 9 (±7 days)	Month 12 (±7 days)	Month 15 (±7 days)	Month 18 (±7 days)
HBV DNA Testing (Japan Only) ⁷	OLE	X	X	X	X	X	X	X
Endoscopic Procedure								
Flexible Sigmoidoscopy/ Colonoscopy (if preferred) ⁸	OLE			X				X
Eligibility Assessment	X							
Randomization	X							
Investigational Product Dispensing	X		X	X	X	X	X	X
Investigational Product Accountability		X	X	X	X	X	X	X
Ulcerative Colitis Assessments								
Bowel Movement Diary Data ⁹	X	X	X	X	X	X	X	X
Partial Mayo Score		X	X		X	X	X	
Mayo Score	OLE			X				X
Contraception Check For Females of Childbearing Potential	X	X	X	X	X	X	X	X
Adverse Event Monitoring	X	X	X	X	X	X	X	X
Concomitant Medication Review	X	X	X	X	X	X	X	X
Risk Factor Check for Venous Thromboembolism ¹¹	X	X	X	X	X	X	X	X

Abbreviations: ET = early termination; β -hCG = beta-human chorionic gonadotropin; OLE = open-label extension study (A3921139).

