9. Bowel movement (BM) diary data will be collected through a phone-based interactive voice recording system (IVRS) tool. Subjects will be instructed in its use at the Baseline visit. Subjects should start completing the BM diary daily approximately 7 days prior to their next scheduled visit. Study site staff should contact the subjects 7 days prior to the scheduled visit to ensure compliance. In addition, subjects should be instructed to start completing the BM diary whenever he/she experiences any worsening of UC symptoms anytime during the study.
10. Demography, including birth date, sex/gender, ethnicity and race will be collected at the Baseline/Day 1 visit and provided in the case report form as allowed by local regulations.
11. **Per Amendment 2, all subjects will be asked at every study visit if they have any newly-developed risk factors for pulmonary embolism as described in [Section 7.3.6](#). At the time of Amendment 2, 138 subjects have been enrolled in the study and have each completed various durations of participation. Per Amendment 3, all subjects will be asked at each applicable visit if they have any newly developed risk factors for venous thromboembolism as described in [Section 7.3.6](#). At the time of Amendment 3, all subjects were enrolled and completed the Month 6 study visit. Therefore, this procedure will only be collected at visits applicable to each subject's individual participation. If a subject has a newly identified risk factor for venous thromboembolism, the subject's tofacitinib dose will be adjusted to open-label 5 mg BID.**

SCHEDULE OF ACTIVITIES (MONTH 21 THROUGH MONTH 42)

Study Procedure	Treatment Period								Follow-Up
	Month 21 (±7 days)	Month 24 (±7 days)	Month 27 (±7 days)	Month 30 (±7 days)	Month 33 (±7 days)	Month 36 (±7 days)	Month 39 (±7 days)	Month 42/ET ¹ (±7 days)	4-weeks after last dose (±7 days)
Visit Number	9	10	11	12	13	14	15	16	17
Targeted Physical Examination ²	X	X	X	X	X	X	X	X	X
Vital Signs, Including Temperature	X	X	X	X	X	X	X	X	X
Laboratory									
Hematology	X	X	X	X	X	X	X	X	X
Serum Chemistry	X	X	X	X	X	X	X	X	X
Lipid Profile, Fasting		X		X		X		X	X
Urine β-hCG ³	X	X	X	X	X	X	X	X	X
Dispense Stool Sample Collection Kit	X	X	X	X	X	X	X		
Collect Stool Sample for Fecal Calprotectin ⁴	X	X	X	X	X	X	X	X	
High-Sensitivity CRP	X	X	X	X	X	X	X	X	
Tuberculosis Testing/Chest Radiograph, if necessary in Specific Countries ⁵		X				X			
HBV DNA Testing (Japan Only) ⁶	X	X	X	X	X	X	X	X	X
Endoscopic Procedure									

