4.1. Inclusion Criteria

Subjects must meet all of the following inclusion criteria to be eligible for enrollment into the study:

1. Subjects currently enrolled in Study A3921139 who have received tofacitinib 10 mg BID for a minimum of 2 consecutive years in Study A3921139 prior to and including baseline of Study A3921288.
2. Subjects who are in stable remission on tofacitinib 10 mg BID for the 6 month period in Study A3921139 up to and including baseline of Study A3921288, defined as meeting all of the following criteria:
 - a. A partial Mayo score ≤ 2 , with no individual subscore > 1 and a rectal bleeding subscore of 0 at each study visit where data is available during the 6 month period in Study A3921139 prior to and including baseline of Study A3921288;
 - b. **AND** at least one assessment of remission based on Mayo score;
 - If an endoscopy was not completed ≤ 6 months prior to baseline of Study A3921288, then an endoscopy performed in Study A3921139 with an endoscopic subscore of 0 or 1, will be required prior to randomization into Study A3921288.
 - All available assessments based on Mayo score during this period must show remission.
 - c. **AND** subjects must not be receiving any corticosteroid therapy for their UC for at least 4-weeks prior to baseline.

3. Female subjects of childbearing potential must agree to use a highly effective method of contraception throughout the study and for at least 28 days after the last dose of assigned treatment. Subjects in Canada who are women of childbearing potential and sexually active must use two contraceptive methods at the same time: one highly effective contraceptive method and one additional effective contraceptive method (see [Section 4.4.4](#)).
4. Female subjects of childbearing potential must have a negative urine pregnancy test prior to randomization.
5. Subjects who are willing and able to comply with scheduled visits, treatment plan, laboratory tests, bowel movement diary calls, and other study procedures.
6. Evidence of a personally signed and dated informed consent document indicating that the subject has been informed of all pertinent aspects of the study.

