6.3. Follow-up Visit (4 weeks after last dose \pm 7 days, Visit 17)

This follow-up visit is to occur 4 weeks (\pm 7 days) after the last dose of investigational product administration.

The following procedures will be performed:

- Targeted physical examination.
- Vital signs, including temperature.
- Laboratory:
 - Hematology.
 - Serum chemistry.
 - Lipid profile, fasting.
 - Urine β -hCG to be performed only for females of childbearing potential.
- Contraception check for females of childbearing potential.
- Adverse event monitoring.
- Concomitant medication review.

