6.4. Subject Withdrawal

Should a subject withdraw from active treatment, the subject should complete the procedures listed at the Month 42/ET Visit. After completing the procedures for the ET visit, the subject should return for a safety evaluation to occur approximately 4 weeks after discontinuing investigational product as per the follow-up visit (see [Section 6.2.9](#)).

Subjects will be withdrawn from the study if any of the following occurs during the study treatment period:

- If rescue therapy is initiated or re-initiated for UC with the exception of oral 5-ASA or sulfasalazine.
- If a subject undergoes surgery for UC.

A subject may be withdrawn from the study for any of the safety concerns as listed in [Appendix 4](#).

If venous thromboembolism is confirmed, discontinue treatment with tofacitinib and withdraw the subject from the study ([Appendix 4](#)).

Subjects who develop a serious infection during the study, defined as any infection (viral, bacterial, and fungal) requiring hospitalization or parenteral antimicrobials or being classified as a serious adverse event should be withdrawn from the study (see [Section 7.3.4](#)).

All abnormal laboratory events of clinical significance should be followed until the laboratory values have returned to normal or baseline levels (see [Appendix 4](#)). Subjects who meet the discontinuation criteria described in [Appendix 4](#) will be withdrawn from the study.

Subjects who are withdrawn from this study will not be permitted to return to Study A3921139.

Withdrawal of consent:

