6.6.1. Adverse Events

The analyses of adverse events under the 3-tier approach described in [Section 3.5](#) is considered exploratory. There will be no adjustment for multiple comparisons or stratification factors in the analyses. For tier-1 events, the proportion of AEs observed in each group will be presented along with the point estimates and associated 95% confidence intervals of the risk difference, and p-value for dose comparison or regimen comparison using the exact methods proposed by Chan and Zhang (1999)² described in [Section 5.2.5](#). For tier-2 events, the proportion of AEs observed in each group will be presented along with the point estimates and associated 95% confidence intervals of the risk difference using the normal approximation for the difference in binomial proportions. In case of zero event rate for tier-2 events in any of group, the 95% confidence intervals will not be computed. AEs will be arranged in the output sorted in descending point estimate of the risk difference within system organ class. Tier 3 AEs will not be summarized separately, they are included

in the overall standard AE summary. Footnotes in the outputs will include the methods used to derive any p-values and confidence intervals as per Pfizer standards.

A listing of subjects with dose reduction due to PE risk factors will be provided.

Incidence Rates (IR) of Adverse Events of Special Interest will be provided. Confidence intervals (95%) will be computed using the exact Poisson method.

For regimen groups, IR will be calculated only for adverse event data for events of special interest only. The numerator will be the number of unique subjects with a treatment emergent event as defined above during the interval from the first dose in A3921288 study to last dose of tofacitinib + 28 days at risk period. The denominator of the incidence rate is person time accruing from the subject's first dose to last dose + 28 days, or to the date of the first event, whichever occurs earlier. For a subject who died, the time will be the minimum of (the date of the last dose + 28 days, or death date).

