For dose groups, IR will be calculated only for adverse events of special interest only. The numerator will be the number of unique subjects with a treatment emergent event as defined above during the interval from the first dose in A3921288 study to dose adjustment for dose escalated or dose reduced subjects otherwise to last dose + 28 days at risk period. The denominator of the incidence rate is person time accruing from the subject's first dose to day of dose escalation, or the first dose to day of dose reduction, or last dose + 28 days, or to the date of the first event, whichever occurs earlier. For a subject who died, the time will be the minimum of dose escalation day, dose reduction day, the day of the last dose + 28 days, or death day.

However, for mortality (death), malignancies (including NMSC), malignancies (excluding NMSC) and MACE related endpoints, all events regardless of their onset within 28 days or beyond after the last dose of tofacitinib will be included. The concept of 28 days is applied to subjects without events that discontinued or completed the study.

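### The only scheduled contact after the last dose may fall up to 7 days before the protocol's 28-day minimum for adverse event collection, while the SAP's incidence rates credit the full 28 days

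*Protocol*

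**What the plan says.** Days below are counted from the last dose unless stated otherwise.

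- **Collection period.** Protocol Section 8.1.4 has AEs and SAEs actively elicited from consent through "a minimum of 28 calendar days; except as indicated below after the last administration of the investigational product". Sections 8.1.4.1 and 8.1.4.2, which follow, neither shorten that period nor add a contact.
- **Last visit.** Protocol Section 6.3 states: "This follow-up visit is to occur 4 weeks", with a 7-day tolerance either way. The Schedule of Activities (Month 21 through Month 42) heads the follow-up column "4-weeks after last dose (±7 days". The introduction to the Schedule of Activities (Baseline through Month 18) adds: "All study visits after Baseline will have a visit window of ± 7 days". It makes no exception for follow-up.
- **Withdrawn subjects.** Under Protocol Section 6.4, "the subject should return for a safety evaluation to occur approximately 4 weeks after discontinuing investigational product as per the follow-up visit".
- **Later contact.** None is scheduled. Appendix 9 allows visits by telephone but adds no contact. Outside the EU, Section 13.2 ends the trial at the last subject's last follow-up visit.
- **At-risk time.** SAP Section 6.6.1 limits incidence rates to adverse events of special interest. For regimen groups, person-time runs from "first dose to last dose + 28 days, or to the date of the first event, whichever occurs earlier", or to death. For dose groups, the interval in which events count runs "to dose adjustment for dose escalated or dose reduced subjects otherwise to last dose + 28 days at risk period", and person-time is cut at the same points. Date of last contact is not among the limits.

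**The concern.** Section 8.1.4 asks for active eliciting, and Section 8.1.2 has each subject questioned about AEs. Once Visit 17 is over, no scheduled procedure does either. A visit on Day 21 satisfies Section 6.3 but leaves a week of the minimum collection period without a planned contact. A new event in that week is recorded only if the subject volunteers it or the site follows up on its own initiative.

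The SAP treats that week as observed. If an event of special interest starts in it and goes unreported, the numerator loses the event while the denominator keeps the time. The error is towards rates that are too low. In relative terms it is largest for subjects who stop early, because the 28 days after the last dose are a larger share of their person-time.

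**Working it through.** **Inputs**
- Minimum collection period: 28 days (Protocol Section 8.1.4).
- Visit 17: 4 weeks ±7 days (Protocol Section 6.3 and Schedule of Activities).
- At-risk credit: last dose + 28 days (SAP Section 6.6.1).
- Subjects: 138, the enrolment stated at Amendment 2 (Protocol Section 9.1).
- Month 42 target: study day 1260 (SAP Appendix 1).

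The documents give no figure of their own for the size of this gap, so there is none to reproduce.

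**Step 1: permitted visit days.** The nominal day is 4 × 7 = 28. The earliest is 28 − 7 = 21 and the latest is 28 + 7 = 35, which gives 15 permitted days. Days 21 to 27 (7 of the 15) precede Day 28; Days 28 to 35 (8 of the 15) do not.

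**Step 2: days without scheduled contact.** Gap = max(0, 28 − visit day). A Day 21 visit gives 28 − 21 = 7 days, and 7/28 = 25% of the minimum period. A Day 27 visit gives 1 day. A visit on Day 28 or later gives 0.

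**Step 3: ceiling over the trial.** If all 138 subjects were seen on Day 21 and none had person-time cut earlier, the gap is 138 × 7 = 966 days, and 966/365.25 = 2.6 person-years. If visit days were instead spread evenly over the window (an assumption), the mean gap is (7+6+5+4+3+2+1)/15 = 28/15 = 1.9 days per subject. The total is then 138 × 28/15 = 258 days, or about 0.7 person-years.

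**Step 4: share of credited person-time.** For T days on treatment and a Day 21 visit, the share is 7/(T + 28):

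| T (days) | 7/(T + 28) | Share |
|---|---|---|
| 30 | 7/58 | 12.1% |
| 90 | 7/118 | 5.9% |
| 180 | 7/208 | 3.4% |
| 540 | 7/568 | 1.2% |
| 1260 | 7/1288 | 0.5% |

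With a constant event rate and nothing captured after the visit, this share is also the largest relative understatement of the rate in subjects with that duration of treatment.

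**Step 5: after the change.** If the last AE contact cannot precede Day 28, the gap is 0. Capping at-risk time at last contact instead would credit 21 days after a Day 21 visit. That removes the SAP mismatch but does not deliver the 28-day collection minimum.

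**The case against.** The strongest reply is that the provisions do not contradict each other. Section 6.3 schedules a visit; it does not end the collection period. A site that sees a subject on Day 21 and then stops collecting breaches Section 8.1.4. This stands: the gap is possible, not built in, and what is missing is a scheduled prompt.

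The consequences are also narrower than they first look:

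- **Person-time.** A reader might infer that every adverse event analysis is affected. It is not. Incidence rates are planned only for events of special interest; the tiered AE analyses use proportions and risk differences. Nor does every event-free subject receive the 28 days: dose-group time is cut at dose change, and all time at death.
- **Death, malignancy and MACE.** SAP Section 6.6.1 counts these whenever they occur, so a late event that becomes known is not lost. Event-free subjects still receive the 28-day credit.
- **Subjects affected.** Those seen on Days 28 to 35 lose nothing. The 7 of 15 is a share of calendar days, not of subjects, and the documents give no distribution of actual visit days.
- **Withdrawals for safety.** One might think the event that led to withdrawal goes unobserved. Section 8.1.4.1 continues follow-up of reported SAEs until they resolve or stabilise, and Section 6.4 does so for clinically significant laboratory abnormalities. Only a new, unvolunteered event is exposed.
- **Comparison of doses.** The window is the same in both arms, and nothing in the documents suggests a difference between them.
- **Pregnancy testing.** Inclusion criterion 3 requires contraception "for at least 28 days after the last dose of assigned treatment", but the protocol does not ask for a test at the end of that period. A last test on Day 21 is therefore not a departure from it.
- **SAP Appendix 1 examples.** The follow-up visits 3 and 6 days after the last dose illustrate how data are assigned to analysis windows. They are not evidence about when visits occur.

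**Conclusion.** The point holds as a small gap between the visit schedule and the protocol's own collection minimum. For subjects seen on Days 21 to 27, between 1 and 7 of the 28 days have no scheduled contact, while the incidence rates of events of special interest count those days as observed. The rates can be slightly understated, with the ceilings worked out above; those ceilings assume every visit on Day 21 and no event captured afterwards.

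The documents do not support a reading in which AE data stop at Day 21, in which 47% of subjects (7/15) are affected, or in which the dose comparison is biased. The case for acting is that the remedy is cheap and makes the schedule deliver what Section 8.1.4 already asks for.

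**What to change.** Either of two changes closes the gap:

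1. Set the Visit 17 window to 28 days after the last dose, 0/+7 days.
2. Keep ±7 days, and require a recorded AE/SAE telephone contact on or after Day 28 whenever the visit is held earlier.

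Make the change in Protocol Section 6.3, in the follow-up column of the Schedule of Activities and in Section 6.4. The general ±7-day statement in the Schedule of Activities needs an exception for Visit 17; otherwise it would contradict a one-sided window. SAP Section 6.6.1 can then keep its 28-day rule.

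The cost is wording in these places, plus slightly less scheduling flexibility for sites or one short call for subjects seen early.

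Separately, and as an editorial point only: Section 6.4 refers to Section 6.2.9 for the follow-up visit. That section describes the on-treatment visits at Months 21 and 33; the reference should be to Section 6.3.
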